8.3.3.3 EXPECTEDNESS

	Number of participants reporting each adverse event (%) [*]	
	10 Hz rTMS group (n=204)	iTBS group (n=208)
Headache	131 (64%)	136 (65%)
Nausea	22 (11%)	14 (7%)
Dizziness	8 (4%)	18 (9%)
Unrelated medical problem†	47 (23%)	46 (22%)
Fatigue	14 (7%)	16 (8%)
Insomnia	14 (7%)	10 (5%)
Anxiety or agitation	8 (4%)	9 (4%)
Back or neck pain	7 (3%)	6 (3%)
Unrelated accidents	2 (1%)	3 (1%)
Vomiting	1 (<1%)	1 (<1%)
Tinnitus	1 (<1%)	3 (1%)
Migraine aura	3 (1%)	4 (2%)
Abnormal sensations	2 (1%)	4 (2%)

rTMS=repulsive transcranial magnetic stimulation. iTBS=intermittent theta burst stimulation. ^{*}p>0.05 on Fisher's exact tests for each pair of proportions.
†Predominantly common infections such as colds and flus.

Table 3: Adverse events

In Table 3 above, there is a list of common, expected AEs⁸⁷. Worsening of any symptoms of depression or related to depression also is an expected AE, as could be the case for any clinical trial of a novel therapy, particularly when there is a sham control condition as in our case. Furthermore, any iTBS study has a risk of mania and hypomania as an expected AE. The study psychiatrist, in accordance with the listed risks on the study ICF, will be responsible for determining whether an adverse event (AE) is expected or unexpected. An AE will be considered unexpected if the nature, severity, or frequency of the event is not consistent with the risk information previously described for the study intervention.

Additional expected potential AEs associated with the intervention and other study procedures include:

- Seizure
- Induction of mania
- Mild pain at site of stimulation
- Anxiety
- Panic
- Symptoms of claustrophobia (feeling fearful, sweating, chills, dizziness, nausea, dry mouth, high heart rate, and high blood pressure)
- Rash, itching, redness, irritation, pain, swelling, and blistering conditions

8.3.4 TIME PERIOD AND FREQUENCY FOR EVENT ASSESSMENT AND FOLLOW-UP

The occurrence of an adverse event (AE) or serious adverse event (SAE) may come to the attention of study personnel during study visits and interviews of a study participant presenting for medical care, or upon review by a study monitor.

All AEs including local and systemic reactions not meeting the criteria for SAEs will be captured on the appropriate electronic case report form (eCRF). Information to be collected includes event description, time of onset, clinician's assessment of severity, relationship to study product (assessed only by those with the training and authority to make a diagnosis), and time of resolution/stabilization of the event. All AEs occurring while on study must be documented appropriately regardless of relationship. All AEs will be followed to adequate resolution or until medical stability as judged by the PD or his designee.

Any medical condition that is present at the time that the participant is screened will be considered as baseline and not reported as an AE. However, if the study participant's condition deteriorates at any time during the study, it will be recorded as an AE.

Changes in the severity of an AE will be documented to allow an assessment of the duration of the event at each level of severity to be performed. AEs characterized as intermittent require documentation of onset and duration of each episode.

Study psychiatrist will record all reportable events with start dates occurring any time after the first study intervention until 30 days following the last day of study intervention. At each study visit, study staff will inquire about the occurrence of AE/SAEs since the last visit. Events will be followed for outcome information until resolution or stabilization.

AEs will be systematically screened for at the start and end of every visit beginning at the active phase of the study (Visit 3). They will be screened for via the following standardized questions that will be asked by research staff:

- Have you had any difficulty with the study interventions?
- Have you had any problems or other things bothering you since our last visit?
- Has anything bothered you enough to...
 - ...prevent you from doing anything you had planned?
 - ...take a prescription or over-the-counter medication or supplement?
 - ...see a medical professional?
 - ...modify the treatment of a pre-existing medical condition?
- Have you been admitted to a hospital or seen in an emergency / urgent care clinic?

Any positive response(s) to the above questions will be documented electronically and further investigated as appropriate. Any documented AE will be asked about at each subsequent AE assessment until it resolves or through the time frame specified above. If an unexpected AE occurs, or if a common AE occurs with severity greater than that expected, the participant will be further evaluated by a member of the study team with formal medical training.

In addition, although the risk of TMS-induced mania is low²¹¹, it will be monitored using the YMRS scale as a solicited event. The scale will be administered at the end of each stimulation day.

AEs will be monitored continuously by designated study staff, recorded in applicable subject-specific and study wide REDCap eCRFs, and reported to the Stanford IRB annually.

Research staff will be trained to attend to signs of AEs and to report any potential unrelated or unexpected AE immediately to the PD. If AEs occur, appropriate medical and/or psychiatric care will be facilitated for the research participant, and recorded in the appropriate electronic AE logs on REDCap. As per Stanford IRB requirements, AEs will be reported to the IRB annually. The NIMH Program Officer will be informed of any actions taken by the IRB as a result of any AEs within 7 business days of notification by the IRB (e.g. study modifications imposed by the IRB).

All subjects will have telephone and email contact information to reach the Protocol Director and the Stanford IRB, in case of any distress or adverse response to rTMS or other components of the study.

All AEs and SAEs will be recorded on the subject-specific and study wide eCRFs, which will be provided to the DSMB on a bi-annual basis. Signs and symptoms will be recorded using standard medical terminology.

The following AE information will be included (when applicable): the specific condition or event and direction of change; whether the condition was preexisting (i.e., an acute condition present at the start of the study or history of a chronic condition) and, if so, whether it has worsened (e.g., in severity and/or frequency); the dates and times of occurrence; severity; causal relationship to the TMS device; action taken; and outcome.

8.3.6 SERIOUS ADVERSE EVENT REPORTING

The PD or his designee will immediately report to the sponsor any serious adverse event (SAE), whether or not considered study intervention related, including those listed in the protocol or investigator brochure, and must include an assessment of whether there is a reasonable possibility that the study intervention caused the event. Study endpoints that are SAEs (e.g., all-cause mortality) must be reported in accordance with the protocol unless there is evidence suggesting a causal relationship between the study intervention and the event. In that case, the investigator will immediately report the event to the sponsor.

All SAEs will be followed until satisfactory resolution or until the site investigator deems either the event is chronic or the participant is stable. Other supporting documentation of the event may be requested by the study sponsor and should be provided as soon as possible.

In case of SAEs, the study investigator will complete an Unanticipated Serious Adverse Event Form and submit to the study sponsor and to the reviewing Institutional Review Board (IRB) as soon as possible, but in no event later than 10 working days after the investigator first learns of the effect. The study sponsor will conduct an evaluation of an unanticipated adverse device effect and will report the results of such evaluation to the Food and Drug Administration (FDA) and to all reviewing IRBs and participating investigators within 10 working days after the sponsor first receives notice of the effect. Thereafter, the

sponsor will submit such additional reports concerning the event as FDA requests. The Investigator will provide all relevant documentation pertaining to an SAE (e.g., additional laboratory tests, consultation reports, discharge summaries, postmortem reports, etc.) to the DSMB and NIMH in a timely manner. Reports relative to the subject's subsequent course will be submitted to the DSMB and NIMH until the event has subsided or, in case of permanent impairment, until the condition stabilizes.

Designated study staff will be responsible for ensuring that unanticipated problems are reported to the IRB in compliance with their requirements for reporting serious and unexpected adverse events. Reporting will be conducted in compliance with guidelines specified by the Stanford University Research Compliance Office.

8.3.7 REPORTING EVENTS TO PARTICIPANTS

At enrollment, participants will be asked whether or not they would like to be informed about study outcomes. We will compile a list of those participants who would like to know about outcomes, and following study completion they will be individually emailed a copy of the study's primary outcome paper using individual, encrypted email.

We will closely monitor AE's on a continuous basis and will involve the independent DSMB in assessing whether any AE is unexpected or more severe than expected (at a rate greater than what would be expected by chance). Should we identify any AE that meets one of those two criteria or should we have any unexpected SAE's, we will notify currently enrolled participants and change our consent to include the pertinent information.

Incidental findings are likely to occur in one of two categories including clinical diagnostic findings and radiographic abnormalities. Should a pertinent clinical diagnostic finding (for instance an interview highly suggestive of occult bipolar disorder), we will inform the participant's psychiatrist. Should an incidental radiographic abnormality be detected during MRI, we will send the imaging to Stanford neuroradiology (as further described in 8.2).

8.3.8 EVENTS OF SPECIAL INTEREST

An adverse event of special interest is a device-specific adverse event designated by the PD for transmission in the same time frame as an SAE, even if it does not meet serious reporting criteria. For this protocol, seizure should be reported as an adverse event of special interest. If there is any doubt whether the information constitutes an SAE, the information should be treated as an SAE for the purpose of this study.

Other reportable information that does not meet the definition of an SAE but is reportable to NIMH and the DSMB with the timeliness of an SAE includes:

- Seizure
- Pregnancy occurring during the study period in which the subject was exposed to the TMS device;
- Overdose (e.g., a dose higher than that prescribed by a healthcare professional for clinical reasons) with or without AEs;
- Abuse (e.g., use for non-clinical reasons) with or without an AE;

- Inadvertent or accidental exposure with or without an AE;
- Device malfunction that would likely result in death, serious injury or other significant adverse event.

8.3.9 REPORTING OF PREGNANCY

We will not include pregnant women in this study. If the participant is of childbearing potential and not already pregnant, the participant must agree to use adequate contraception (hormonal / barrier method of birth control or abstinence) prior to study and for the duration of the study participation. During the screening phase of this study, participants of childbearing potential will be administered a pregnancy test; a negative pregnancy test will be required to confirm eligibility for study participation and will be completed prior to their receiving any rTMS stimulation. If a participant becomes pregnant or suspects she is pregnant while participating in the aiTBS stimulation week of the study, she should inform the research staff immediately via in-person meeting, telephone call, or email. If a participant reports pregnancy occurring during the study period in which the participant was exposed to the rTMS stimulation, research staff will stop rTMS stimulation and then notify the Protocol Director.

8.4 UNANTICIPATED PROBLEMS

8.4.1 DEFINITION OF UNANTICIPATED PROBLEMS (UP)

The Office for Human Research Protections (OHRP) considers unanticipated problems involving risks to participants or others to include, in general, any incident, experience, or outcome that meets all of the following criteria:

- Unexpected in terms of nature, severity, or frequency given (a) the research procedures that are described in the protocol-related documents, such as the Institutional Review Board (IRB)-approved research protocol and informed consent document; and (b) the characteristics of the participant population being studied;
- Related or possibly related to participation in the research (“possibly related” means there is a reasonable possibility that the incident, experience, or outcome may have been caused by the procedures involved in the research); and
- Suggests that the research places participants or others at a greater risk of harm (including physical, psychological, economic, or social harm) than was previously known or recognized.

This definition could include an unanticipated adverse device effect, any serious adverse effect on health or safety or any life-threatening problem or death caused by, or associated with, a device, if that effect, problem, or death was not previously identified in nature, severity, or degree of incidence in the investigational plan or application (including a supplementary plan or application), or any other unanticipated serious problem associated with a device that relates to the rights, safety, or welfare of subjects (21 CFR 812.3(s)).

8.4.2 UNANTICIPATED PROBLEM REPORTING

The investigator will report unanticipated problems (UPs) to the reviewing Institutional Review Board (IRB). The UP report will include the following information:

- Protocol identifying information: protocol title and number, PD's name, and the IRB project number;
- A detailed description of the event, incident, experience, or outcome;
- An explanation of the basis for determining that the event, incident, experience, or outcome represents an UP;
- A description of any changes to the protocol or other corrective actions that have been taken or are proposed in response to the UP.

To satisfy the requirement for prompt reporting, UPs will be reported using the following timeline:

- UPs that are serious adverse events (SAEs) and/or result in unexpected deaths or life-threatening experiences related to the research will be reported to the IRB and to the Data Safety Monitoring Board (DSMB) within 10 days of the investigator becoming aware of the event.
- Any other UP will be reported to the DSMB within 30 days of the investigator becoming aware of the event and subsequently reported to the IRB within 10 working days from receiving assessment from the DSMB.
- All UPs should be reported to appropriate institutional officials (as required by an institution's written reporting procedures), the supporting agency head (or designee), and the Office for Human Research Protections (OHRP) within 30 days of the IRB's receipt of the report of the problem from the investigator.

An investigator shall submit to the sponsor and to the reviewing IRB a report of any unanticipated adverse device effect occurring during an investigation as soon as possible, but in no event later than 10 working days after the investigator first learns of the effect (21 CFR 812.150(a)(1)). A sponsor who conducts an evaluation of an unanticipated adverse device effect under 812.46(b) shall report the results of such evaluation to the Food and Drug Administration (FDA) and to all reviewing IRB's and participating investigators within 10 working days after the sponsor first receives notice of the effect. Thereafter the sponsor shall submit such additional reports concerning the effect as FDA requests (21 CFR 812.150(b)(1)).

8.4.3 REPORTING UNANTICIPATED PROBLEMS TO PARTICIPANTS

Should an unanticipated problem occur (such as identifying an AE that is more common or severe than expected, or a data breach of any sort), the investigators will inform those participants that have been affected of both the problem and any proposed solution. Should the unanticipated problem have the potential to affect future participants it will be added to the consent document.

9 STATISTICAL CONSIDERATIONS

9.1 STATISTICAL HYPOTHESES

- Primary Mechanistic Endpoint:

We hypothesize that the reduction in resting-state functional connectivity between the subgenual anterior cingulate cortex and the default mode network from baseline through intervention day 5 will be significantly greater for participants receiving active as compared to sham aiTBS.

- Secondary Mechanistic Endpoints:
 - (a) We hypothesize that there will be a significantly greater association between the change in depression symptoms (as measured by the MADRS-S) and the change in resting-state functional connectivity between the subgenual anterior cingulate cortex and the default mode network from baseline to after intervention day 5 for participants receiving active as compared to sham aiTBS.
 - (b) We hypothesize that there will be a significantly greater association between acute mood state (as measured by the IMS-12) and the change in resting-state functional connectivity between the subgenual anterior cingulate cortex and the default mode network from baseline to after intervention day 5 for participants receiving active as compared to sham aiTBS.

9.2 SAMPLE SIZE DETERMINATION

Sample size justification (power analysis):

Key Hypothesis of the study: A significant reduction in functional connectivity between sgACC and DMN. We hypothesize that the reduction in functional connectivity between the subgenual cingulate cortex and the default mode network from baseline to after intervention day 5 will be significantly greater for participants receiving active compared to sham aiTBS. Several past studies have found no significant changes in functional connectivity with sham rTMS targeted to DLPFC^{136,212}. Using preliminary data from our open-label study of aiTBS for treatment of severe depression, there was an effect size of 1-1.47 (depending on DMN node) for change in connectivity between sgACC and DMN¹⁵⁰. One potential approach for determining the power calculation would be that considering we will have 10 unique comparisons with each day's data be compared to every other day over 5 days, and that we will be comparing across 4 DMN nodes and 2 sgACC nodes, our target alpha needs to be $0.05/(10*4*2) = 0.000625$. Thus, for an effect size of 1, alpha of 0.000625, and a power of 0.80, and powering for an independent-measures t-test, 40 participants will be required for each arm. Regarding our secondary mechanistic endpoints, we have previously found a significant correlation between change in FC between sgACC and DMN in participants receiving open-lab aiTBS, Pearson $r = 0.51$. For a point biserial model, a two-tailed 2 test, and a power target of 0.80, 25 participants will be required for each group.

Our recruitment goals are based on our primary mechanistic endpoint. Considering a ~25% attrition rate (combined participants lost to followup and unusable or missing scans), **we plan to recruit 50 participants in each arm**, as this is larger than the 18 per arm that is required to power for a significant reduction in IMS-12, and large enough to provide sufficient power for our secondary mechanistic endpoints. Given that there are ~1,000 new depressed patients at Stanford per year, >75% are TMS-naïve, there are many more than 100 patients per year that meet inclusion criteria.

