9.4.3 ANALYSIS OF THE SECONDARY ENDPOINT(S)

Our secondary hypotheses are:

- (a) We hypothesize that there will be a significantly greater association between the change in depression symptoms (as measured by the MADRS-S) and the change in resting-state functional connectivity between the subgenual anterior cingulate cortex and the default mode network from baseline to after intervention day 5 for participants receiving active as compared to sham aiTBS.
- (b) We hypothesize that there will be a significantly greater association between acute mood state (as measured by the IMS-12) and the change in resting-state functional connectivity between the subgenual anterior cingulate cortex and the default mode network from baseline to after intervention day 5 for participants receiving active as compared to sham aiTBS.

We will use fMRI to measure resting-state FC between sgACC & DMN. Participants will be treated for 5 consecutive days with 10 sessions per day of active or sham aiTBS. Participants have a baseline MRI scan prior to each day of aiTBS intervention as well as the day following the completion of intervention. After standard preprocessing of fMRI data, we will calculate FC as the correlation of the activity pattern across time between the sgACC and DMN regions of interest. All correlation coefficients will then be transformed into Fisher's Z score for further analysis.

MADRS-S will be collected at baseline, the end of each intervention day, and the day following intervention. IMS-12 will be collected at baseline, on the morning of each intervention day, and the day following intervention.

Normality in change in both assessments and change in FC from baseline to post-intervention will be assessed via Shapiro-Wilk. Appropriate correlational analysis (Pearson or Spearman) will be used to quantify the association between change in FC and change in each assessment for each treatment group. Correlation coefficients will be compared statistically by performing Fisher's R-to-Z transformation and the difference between the two Z-scores will be tested for statistical significance using a two-tailed Z-test with an alpha level of 0.05 ($p < 0.05$). The null hypothesis, i.e. no difference in the association between change in FC and change in each assessment between groups, will be rejected if the Z-test has a p-value < 0.05 .

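### The 25 per group for the secondary endpoints sizes a test of one correlation against zero, not the planned comparison of two arms' correlations, so the sufficient-power statement does not hold unless the sham correlation is negative

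*Combined protocol and SAP*

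**What the plan says.** Section 9.2 takes a Pearson correlation of 0.51 from the group's open-label work and states: "For a point biserial model, a two-tailed 2 test, and a power target of 0.80, 25 participants will be required for each group". It then sets recruitment at 50 per arm, allowing for roughly 25% attrition from loss to follow-up and unusable or missing scans, and describes that number as "large enough to provide sufficient power for our secondary mechanistic endpoints". The same section says that the recruitment target rests on the primary endpoint.

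Section 9.1 frames both secondary hypotheses (MADRS-S and IMS-12) as a stronger association with connectivity change "from baseline to after intervention day 5 for participants receiving active as compared to sham aiTBS". Section 9.4.3 gives the test. A Pearson or Spearman correlation is computed in each arm and put on the Fisher scale, after which "the difference between the two Z-scores will be tested for statistical significance using a two-tailed Z-test with an alpha level of 0.05". Equality of the two arms is the hypothesis at stake, worded there as "no difference in the association between change in FC and change in each assessment between groups, will be rejected if the Z-test has a p-value" below 0.05.

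No sham-arm correlation is given anywhere. The nearest text is in Section 9.2: "Several past studies have found no significant changes in functional connectivity with sham rTMS targeted to DLPFC". That concerns the mean change in connectivity under sham, not its correlation with mood change.

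**The concern.** The sample-size sentence and the analysis section describe two different tests. A single correlation of 0.51 against zero is an easier target than a difference between two estimated correlations: on the Fisher scale the difference has variance 2/(n−3), twice that of one correlation. If 25 per group answers the easier question, the plan has no stated power for the test that it will run, and its assurance about the secondary endpoints has no basis. These two comparisons are the plan's formal between-arm tests, outside the exploratory analyses, of whether connectivity change tracks clinical change. A team relying on Section 9.2 would overestimate its chance of detecting the difference.

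**Working it through.** **Inputs from the documents.** Active-arm r = 0.51 (9.2); two-tailed test with power 0.80 (9.2); alpha 0.05 (9.4.3, since the sample-size sentence gives none); 1:1 allocation (6.3); 50 recruited per arm and about 25% attrition (9.2). Evaluable per arm after attrition: 50 × 0.75 = 37.5. The plan's own primary requirement is 40, so 37–40 is used.

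**Input not in the documents.** The sham-arm correlation. It is taken as 0, with −0.2 to +0.2 shown. Signs are relative to the active arm.

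**Step 1: reproduce the stated 25.** Point-biserial test of one correlation against zero: noncentral t, N−2 degrees of freedom, noncentrality √(N·r²/(1−r²)). At N = 25 the noncentrality is √(25 × 0.2601/0.7399) = 2.96. Two-sided power is 0.793 at N = 24 and 0.810 at N = 25, so 25 reproduces exactly. A one-sided version gives 20. The Fisher-z formula for one correlation gives 28 two-sided and 23 one-sided.

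**Step 2: sample size for the planned test.** On the Fisher scale, atanh(0.51) = 0.5627 and atanh(0) = 0.

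n per arm = 2 × ((1.960 + 0.842)/(0.5627 − 0))² + 3 = 52.6, so 53 evaluable per arm.

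**Step 3: power of the planned test.** Power = Φ(difference/√(2/(n−3)) − 1.960), plus a negligible opposite tail. With sham r = 0:

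- n = 25: 0.5627/0.3015 = 1.866, power 0.463
- n = 37: 0.5627/0.2425 = 2.320, power 0.641
- n = 40: 0.5627/0.2325 = 2.420, power 0.677
- n = 50: 0.5627/0.2063 = 2.728, power 0.779

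Simulation with 60,000 replicates per n gives 65% at 37, 69% at 40, 79% at 50, 80% at 52 and 81% at 53, so the approximation is sound.

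**Step 4: sensitivity to the sham correlation (active r = 0.51).**

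| Assumed sham r | Power, n = 25 | n = 37 | n = 40 | n = 50 | n per arm for 80% |
|---|---|---|---|---|---|
| −0.2 | 0.719 | 0.884 | 0.909 | 0.960 | 30 |
| −0.1 | 0.595 | 0.781 | 0.814 | 0.895 | 39 |
| 0 | 0.463 | 0.641 | 0.677 | 0.779 | 53 |
| +0.1 | 0.335 | 0.479 | 0.512 | 0.611 | 77 |
| +0.2 | 0.223 | 0.317 | 0.341 | 0.415 | 125 |

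**Step 5: where 80% is reached.** Solving 0.5627 − atanh(sham r) = 2.802 × √(2/(n−3)) gives a sham correlation of about −0.02 at n = 50, −0.09 at n = 40 and −0.12 at n = 37. Alternatively, with sham r = 0, the active-arm correlation would have to be 0.52 at 50, 0.57 at 40 or 0.59 at 37.

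If Spearman is used, with an assumed variance factor of 1.06, the requirement at sham r = 0 becomes 2 × 1.06 × (2.802/0.5627)² + 3 = 55.5, so 56 per arm.

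**The case against.** **The 25 is not a miscalculation.** This stands. It is correct for the test it describes, and at 37–40 per arm a single correlation of 0.51 would be detected with 91–93% power (Fisher-z). But Section 9.4.3 uses the within-arm correlations only as ingredients; its null is about their difference.

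**Recruitment rests on the primary endpoint.** This also stands. The primary requirement of 40 per arm reproduces (power 0.81 at alpha 0.000625 and effect size 1). A reader might infer that the trial is too small, or must recruit 53/0.75 = 71 per arm. The documents do not support that, because the secondary endpoints do not set the sample size.

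**The 53 depends on an outside assumption.** Correct. It should not be read as a fixed requirement: a sham correlation of −0.1 brings it to 39. Zero is a natural planning value, but it is not a worst case, since any positive value raises the number.

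**Attrition may be made good.** Sections 7.1 and 7.2 allow withdrawn participants to be replaced, including treated participants who leave before completing all scans. A reader might take 64–68% as the settled power; it is the lower end of a range whose upper end, with full replacement, is 78%. Replacement is optional, however, and does not clearly cover unusable scans from participants who complete. Section 9.3 also restricts these analyses to a per-protocol set.

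**A model using the daily data might be preferred.** A reader might infer that the Fisher-z test should be replaced by a mixed model of daily mood on daily connectivity. The documents do not support that as a correction. The stated hypotheses concern change from baseline to after day 5. The Schedule of Activities uses the standard MADRS-S at Visit 3 and the 24-hour version at Visits 4–8. Section 9.4.3 places MADRS-S at the end of each intervention day, whereas scans are in the morning. No power has been computed for such a model.

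**Conclusion.** The mismatch is real. Section 9.2 powers one correlation against zero, and Section 9.4.3 tests a difference between two. With an active-arm correlation of 0.51 and an assumed sham correlation of 0, the planned test misses the plan's 80% target at every number of participants the plan can expect, narrowly with no net loss and clearly after the stated attrition. The adequacy statement could hold only with a sham correlation opposite in sign to the active arm's, which the plan never assumes.

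The conclusion rests on the 0.51 as given. The sentence that reports it names only connectivity change and not the variable it was correlated with, so its relevance to MADRS-S or IMS-12 cannot be confirmed. The fault is confined to the secondary-endpoint power statement and should be corrected; the primary sample size, the design and the choice of secondary test are not affected. That a null secondary result would be misread as evidence against the mechanism is a possible consequence, but nothing in the documents says it would be interpreted that way.

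**What to change.** In Section 9.2, replace the 25-per-group sentence with the power of the two-tailed Fisher-z difference test at alpha 0.05, for 37 to 50 evaluable participants per arm, an active-arm correlation of 0.51 and a range of sham-arm correlations explicitly labelled as assumptions; the Step 4 table can be used directly. State that the lower end reflects the planned attrition and the upper end full replacement under Sections 7.1 and 7.2. Delete the claim of sufficient power for the secondary endpoints. Name the two variables behind the 0.51.

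Keep the prespecified Fisher-z comparison as the secondary analysis. The cost is an amendment to wording, best made before unblinding. It needs no extra participants, data or programming; the stated power simply becomes less favourable.
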